A single-center randomized, double-blind controlled trial of  
Transcutaneous Vagus Nerve stimulation (ta-VNS) for improvement  
of upper extremity motor function in stroke patients

Title	A single-center randomized, double-blind controlled trial of Transcutaneous Vagus Nerve stimulation (taVNS) for improvement of upper extremity motor function in stroke patients
Application	Department of Rehabilitation, Zhujiang Hospital, Southern Medical University
Purpose	Primary objectives: To investigate the facilitative effect of transcutaneous auricular vagus nerve stimulation with upper limb motor rehabilitation training on the improvement of upper limb motor function in stroke. Secondary objective: To examine the necessity of pairing with motor function training for transcutaneous auricular vagus nerve stimulation to improve upper limb dysfunction in stroke.
Research hypothesis	1) The test group will show significantly greater improvement in upper limb motor function in stroke patients compared to the control group. 2) Upper limb motor rehabilitation training paired with transcutaneous auricular vagus nerve stimulation will be significantly more effective in improving upper limb motor function in stroke patients compared with the unpaired test group.
Design	Exploratory single-center, double-blind, randomized controlled trial
Sample size	Sample size was determined: $n = 2 * [(Z\alpha + Z\beta)\sigma/d]^2$ (sample size estimated using the statistical effect force analysis software G*Power3.1). The sample size for this study was estimated as 40 study patients per group based on the effect size (effect size, Cohend's $d = 0.632$ ) and $\alpha = 0.05$ , $\beta = 0.80$ from the trial by Dawson et al. (2021). The sample size was adjusted to 50 patients per group based on the clinical sample dropout rate (20%). The final study population was 150 patients with ischemic stroke. Of these, 50 received upper extremity motor rehabilitation paired with transcutaneous auricular vagal stimulation, 50 received upper extremity motor rehabilitation with unpaired transcutaneous auricular vagal stimulation, and 50 received upper extremity motor rehabilitation paired with sham-stimulation (control group).

Eligibility	
Inclusion Criteria:
 

- Patients diagnosed with stroke according to a clinically qualified physician with reference to the Chinese Stroke Prevention and Control Guideline (2021)

- Patients in the acute/recovery phase (after 2 weeks of onset) with stable signs

- No previous neuropsychiatric-related diseases

- No significant impairment of cognitive function and able to cooperate in completing the corresponding rehabilitation training

- With unilateral upper limb dysfunction

- Male or female, 18-80 years of age

- Patients who have not received various neuromodulation rehabilitation treatments

- No contraindications to taVNS

- Subjects voluntarily cooperate with the study and agree to sign an informed consent

 
Exclusion Criteria:
 

- Patients have other mental health disorders (dementia, Parkinson's disease, depression, schizophrenia, bipolar disorder, etc.)

- Patients have uncontrolled epilepsy, i.e., having had a seizure within 4 weeks prior to enrollment

- Patients have cardiac arrhythmias or other abnormalities

- Patients have a history of respiratory disease or disorder, including pneumonia, dyspnea and asthma

- The presence of gastrointestinal disorders such as diarrhea and vomiting that make it difficult for the patient to cooperate

- Patients have a history of vasovagal syncope

- Patients are under treatment with other neurostimulation/modulation

- The presence of severe spasticity, other serious injuries to the upper extremities, or other medical conditions

- Patients have difficulty in understanding and communication, so they can't complete the test

- Women who are pregnant or breastfeeding

Major interventions	
1) Paired taVNS:
 
-Intervention: Upper extremity motor rehabilitation training will be conducted with paired taVNS. The stimulator will be placed on the left ear of the patient. While the patient performs the action training, the EMG signal feature caused by the action will trigger an electrical stimulation of the transcutaneous auricular vagus nerve. The amplitude of the electrical stimulation will be adjusted under patients' pain threshold. The intervention will be performed once a day for 40-60 minutes for 14 days.

	
2) Unpaired taVNS: -Intervention: Upper extremity motor rehabilitation training will be conducted with unpaired taVNS. The stimulator will be placed on the patient's left ear. Patients will receive 30 minutes of stimulation, with pulses of 500 ms occurring every 5-7 seconds. A total of 300 stimulations will be completed with pulses of 500 ms. After that motor training will be performed. The motor training will be identical to that of the paired group. The amplitude of the electrical stimulation will be adjusted under patients' pain threshold. The intervention will be conducted once a day, with 30 minutes of stimulation followed by 30 minutes of motor training each time for 14 days.
 
3) Sham taVNS: Upper limb motor rehabilitation training will be conducted with paired taVNS sham-stimulation. The stimulator will be placed on the patient's left ear. The amplitude of the electrical stimulation will be adjusted at 0 mA. The intervention will be conducted once a day for 40-60 minutes for 14 days.

Evaluating indicator	
Primary outcome: The score of Fugl-Meyer Assessment of Upper Extremity (FMA-UE) will be tracked before and after the intervention in the paired taVNS, unpaired taVNS, and sham taVNS groups.
 
Secondary outcome: Changes in ADL (Modified Barthel Index), the Hong Kong version of the Functional Test for the Hemiplegic Upper Extremity (FTHUE-HK), Wolf Motor Function Test (WMFT), EEG, and EMG features will be tracked after the intervention among participants.

Statistical method	
1. Primary endpoints: ANOVA, paired-sample t-test, and independent-sample t-test will be used.
 
(1) For the main efficacy index FMA-UE scores, paired sample t-test will be performed before and after the intervention to compare whether there will be a significant change before and after the intervention. Since this statistical operation is based on multiple comparisons, there may be a bias of alpha inflation. Therefore, the statistical results will be corrected based on Bonferroni's principle.
 
(2) The FMA-UE scores before and after the intervention will be summed and subtracted to obtain the FMA-UE change scores of the indicators before and after the intervention (i.e., the main intervention effect), and a one-way three-level (paired vs. unpaired vs. pseudo-stimulated) analysis of variance (ANOVA) will be performed on the main intervention effect of the three groups to obtain the variability of the main intervention effect of the three groups.
 
(3) Independent samples t-tests will be conducted for the main intervention effects among groups. The main intervention effects of the two experimental groups will be obtained. And the main intervention effects of the paired experimental group and the unpaired experimental group will be compared by independent sample t-test.

	
2. Secondary endpoints: ANOVA, paired samples t-test, independent samples t-test
 
(1) Paired-samples t-tests will be performed before and after the intervention for WMFT, Brunnstrom scale, Modified Barthel Index, FTHUE-HK, and EMG characteristics to compare whether there will be significant changes before and after the intervention. Since this statistical manipulation is based on multiple comparisons and there would be a bias for alpha inflation, and the statistical results will be corrected based on Bonferroni's principle.
 
(2) The WMFT, Brunnstrom scale, Modified Barthel Index, FTHUE-HK, and EMG characteristics before and after the intervention were summed and subtracted. To obtain the WMFT, Brunnstrom assessment, ADL, FTHUE-HK, and changes in EMG characteristics of the indicators before and after the intervention (i.e., secondary intervention effects), and the secondary intervention effects of the three groups were subjected to a one-way three-level (paired vs. unpaired vs. pseudo-stimulation) multiple test analysis of variance (Multivariate ANOVA) to obtain the variability of the secondary intervention effects in the three groups.
 
3) The WMFT, Brunnstrom scale, Modified Barthel Index, FTHUE-HK, and change in EMG characteristics of the paired and unpaired test groups will be tested by independent samples t-tests to obtain the difference of secondary intervention effects between paired and unpaired groups. To compensate the alpha inflation bias, the statistical results will be corrected based on Bonferroni's principle.

--	--

#Table 1 Schematic timeline of the study

TIMEPOINT	Enrollment	Allocation	Post-Allocation				Close-out
	ts	t0	t1	t2	t3	t4	t5
Enrolment	×						
Eligibility screen	×						
Informed consent	×						
Demographic information	×						
Medical history	×						
Vital signs	×		×	×	×	×	×
Randomization		×					
Allocation		×					
Interventions							
Paired ta-VNS				×			

ta-VNS	×						
Sham ta-VNS	×						

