**Assessments**

FMA-UE	×		×	×	×		
WMFT	×		×	×	×		
Brunnstrom	×		×	×	×		
Modified Barthel Index	×		×	×	×		
FTHUE-HK	×		×	×	×		
Adverse events		×	×	×	×	×	×

- 1) Demographic information includes the patients date of birth, sex and race;
- 2) Medical history includes stroke and other clinically significant past and present medical history and pre-existing/combined medications;
- 3) Vital signs include blood pressure, pulse rate, respiration and body temperature;

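### The primary FMA-UE analysis uses arm as its only factor, although entry covers a recovery phase with no numeric end; adjusting for time since onset would gain precision at almost no cost.

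*Protocol*

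**What the plan says.** **Entry.** The inclusion criteria in the Protocol synopsis (Eligibility) admit "Patients in the acute/recovery phase (after 2 weeks of onset) with stable signs". The only number is the 2-week floor. The phase is named but not defined in days or months, and no other inclusion or exclusion criterion limits time since onset.

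**Endpoint.** Under Evaluating indicator, "The score of Fugl-Meyer Assessment of Upper Extremity (FMA-UE) will be tracked before and after the intervention" in the three groups. The treatment period is 14 days (Major interventions: "The intervention will be performed once a day for 40-60 minutes for 14 days" for the paired arm, with the same number of days in the other two).

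**Analysis.** Statistical method, item 1, names three steps for FMA-UE:
- Before-after comparison: "paired sample t-test will be performed before and after the intervention to compare whether there will be a significant change".
- Comparison of change across the three arms: "a one-way three-level (paired vs. unpaired vs. pseudo-stimulated) analysis of variance (ANOVA) will be performed on the main intervention effect".
- Pairwise comparison: "Independent samples t-tests will be conducted for the main intervention effects among groups".

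Arm is the only factor in the between-arm steps, and no covariate is named.

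**Data.** Table 1 lists randomization and allocation as timeline rows without describing a method. Its notes say "Medical history includes stroke and other clinically significant past and present medical history". Time since onset appears nowhere outside the inclusion criterion.

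**The concern.** The quantity that the protocol calls the main intervention effect is the raw FMA-UE change over the treatment period, so it includes whatever the patient would have recovered untreated. How much that is depends on how long ago the stroke occurred. This is general clinical knowledge; the documents do not quantify it. If the sample mixes patients a few weeks after onset with patients well past that, part of the spread in change scores reflects time since onset rather than treatment or noise.

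A model with arm alone leaves that part in the error term. This has two consequences. The paired-versus-sham and paired-versus-unpaired contrasts are estimated less precisely than the data allow. And if one arm happens to receive more early patients, the estimate moves with the imbalance and the stated tests cannot move it back. Baseline FMA-UE does not fully stand in for time since onset, because two patients with the same score at different times after onset can have different expected change.

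**Working it through.** **1. The plan's own figure.** Inputs from the Protocol (Sample size): d = 0.632, α = 0.05, and the stated 0.80 read as power. With two-sided α:

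n = 2 × [(1.960 + 0.842)/0.632]² = 39.3, so 40 per group; 40/(1 − 0.20) = 50 per group.

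Both stated figures reproduce. The exact power of a two-sided t-test at 40 per group (noncentral t) is 0.797.

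**2. Assumptions, none of them from the documents.** SD of FMA-UE change 6 points, so that d = 0.632 corresponds to 0.632 × 6 = 3.8 points. Half the patients are early and half late (q = 0.5). Spontaneous 14-day change differs between early and late patients by D = 2, 4 or 6 points. The phase variance is taken to lie inside the total variance of 36.

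**3. Variance due to phase, and power if it is removed.** Phase variance = q(1 − q)D². Residual SD = √(36 − phase variance). Rescaled d = 0.632 × 6/residual SD.

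| D (points) | Phase variance | Share of 36 | Residual SD | Rescaled d | Power, 40 per arm |
|---|---|---|---|---|---|
| 2 | 1 | 3% | 5.92 | 0.641 | 0.808 |
| 4 | 4 | 11% | 5.66 | 0.670 | 0.842 |
| 6 | 9 | 25% | 5.20 | 0.730 | 0.897 |

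These powers ignore the degree of freedom spent on the covariate and assume that the model captures phase completely, so they are slightly favourable.

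**4. Chance imbalance.** The SD of the difference between two arms in the share of early patients is √(2 × 0.25/40) = 0.112. At the 95% limit, 1.96 × 0.112 × D shifts an arm contrast by 0.44, 0.88 or 1.31 points, which is 12%, 23% or 35% of 3.8. In simulation of simple randomisation with a 50:50 mix, two given arms differ by at least 15 percentage points in about 22% of trials and by at least 20 points in about 9%.

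**5. Is that shift already allowed for?** The unadjusted 95% half-width of an arm contrast is 1.96 × 6 × √(2/40) = 2.63 points. The shifts in step 4 are about one-sixth, one-third and one-half of it and lie within it, because the unadjusted SD of 6 contains the phase variance. With the residual SDs of step 3 the half-width becomes 2.59, 2.48 or 2.28 points.

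**6. Sensitivity to the split.** q = 0.5 maximises q(1 − q). At q = 0.3 the factor is 0.21, and the shares become 0.84/36 = 2%, 3.36/36 = 9% and 7.56/36 = 21%.

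**7. Sensitivity to where the variance sits.** The documents do not say whether the SD behind d = 0.632 already contains variance due to time since onset. If that variance comes on top, and makes up 10%, 20% or 30% of the new total, d is multiplied by √(1 − share). Unadjusted power at 40 per group then falls to 0.754, 0.704 or 0.646. This is a separate scenario and is not added to step 3.

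**The case against.** The strongest reply is that the plan is valid as it stands. Randomisation with a concurrent sham arm keeps the contrasts unbiased, the unadjusted standard error already covers chance imbalance (working, step 5), and the trial calls itself exploratory. All of that is right. What remains is a gain in precision not taken. It is still worth taking, because the trial is sized at about 0.80 power with no margin and states two superiority hypotheses.

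The sizes can also be challenged. The SD, the mix and D are assumed, and the 50:50 split is the most favourable one. D = 6 requires an early-late difference in spontaneous change larger than the whole 3.8-point target. At D = 2 the gain is negligible. This stands and limits how much weight the upper figures can bear.

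Four stronger readings are tempting, and the documents do not support them:
- *Entry has no upper limit on time since onset.* The criterion restricts entry verbally to a phase. What is missing is a numeric end or definition. Whether patients a year after onset would qualify cannot be told from the text.
- *Allocation ignores time since onset.* No allocation method is described, so stratification may be specified elsewhere. Silence does not show its absence.
- *The between-arm results would be biased.* They would not be; an imbalance in one trial is chance error that the test allows for. Only the within-arm paired t-tests mix treatment effect with spontaneous recovery, and those do not compare arms.
- *The trial is underpowered for this reason.* That follows only if the phase variance lies outside the SD behind d = 0.632, which the documents do not settle.

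**Conclusion.** The point holds as one about the analysis model. It rests on stated text: the protocol itself fixes a one-way ANOVA and t-tests on raw FMA-UE change with arm alone, while admitting patients from a phase whose end is not given in numbers. The between-arm tests remain unbiased with correct type I error; the cost is precision and an inability to correct chance imbalance.

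Under SD 6, a 50:50 mix and 40 evaluable per arm, with phase variance inside the planned SD, adjustment raises power from 0.80 to about 0.81, 0.84 or 0.90 for early-late differences of 2, 4 or 6 points. The benefit therefore runs from negligible to material, and the documents cannot say where in that range the trial lies. The change is worth making because it costs so little.

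**What to change.** In Statistical method, item 1, replace the arm-only ANOVA and the between-arm t-tests on FMA-UE with one pre-specified linear model containing arm and time since onset at entry, with baseline FMA-UE as a further covariate. Take the paired-versus-sham and paired-versus-unpaired contrasts from that model. Fix the form in which time since onset enters (continuous, transformed or categories) before unblinding.

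The cost is one or two model terms. The onset date is already needed to apply the 2-week criterion, and baseline FMA-UE is already scheduled at enrolment in Table 1. No added patients, visits or assessments are needed, and the change can be made after recruitment has begun.

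Optional: if the allocation list is not yet fixed and is not already stratified, stratify it by time since onset. The model term alone gives most of the gain.

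### The unpaired arm's motor training is called identical to the paired arm's, but the stated times do not show it, so the test of pairing may be confounded with amount of training

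*Protocol*

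**What the plan says.** All the relevant text is in the protocol's synopsis table.

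- **Major interventions, 1) Paired taVNS.** Stimulation takes place during training: "While the patient performs the action training, the EMG signal feature caused by the action will trigger an electrical stimulation". The duration is given for the intervention as a whole: "The intervention will be performed once a day for 40-60 minutes for 14 days". No separate stimulation block or set-up period is described.
- **Major interventions, 2) Unpaired taVNS.** Stimulation comes first, and then "After that motor training will be performed". The comparability statement is "The motor training will be identical to that of the paired group". The daily schedule is "with 30 minutes of stimulation followed by 30 minutes of motor training each time for 14 days".
- **Major interventions, 3) Sham taVNS.** This arm is described as paired with sham stimulation and has the same length as the paired arm: "The intervention will be conducted once a day for 40-60 minutes for 14 days".
- **Purpose, secondary objective.** "To examine the necessity of pairing with motor function training". Hypothesis 2 states that the paired arm will be superior to the unpaired arm.
- **Statistical method, primary endpoints, item (3).** On FMA-UE change, "the main intervention effects of the paired experimental group and the unpaired experimental group will be compared by independent sample t-test". Item 3 under the secondary endpoints repeats the comparison for the other scales and the EMG measures.

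**The concern.** The unpaired arm exists to isolate one factor, the timing of stimulation relative to movement. That works only if the paired and unpaired arms otherwise receive the same rehabilitation. The protocol asserts this, but the times it gives do not bear it out: 30 minutes of training in one arm, and in the other a 40-60 minute session in which training with triggered stimulation is the only activity described.

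Read naturally, the two arms differ in amount of motor training as well as in pairing. The intervention is motor training and the outcome is motor function, so extra training in the paired arm is a rival explanation for a result in favour of hypothesis 2. An unpaired-versus-sham contrast would be affected the other way, because sham has the longer session and the unpaired arm could look worse than it is. Analysis would not cleanly repair this: if training time is set by arm, adjustment cannot separate it from pairing.

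**Working it through.** **Inputs (Protocol, Major interventions)**

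- Unpaired: 30 min stimulation, then 30 min training; 14 days; 300 stimulations, one every 5-7 s.
- Paired and sham: 40-60 min intervention; 14 days.
- Non-training minutes within a paired or sham session: not stated. Call this *s* and vary it from 0 to 30.

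**Step 1: the plan's own figure for the unpaired stimulation block.** 300 × 5 s = 25 min, 300 × 6 s = 30 min and 300 × 7 s = 35 min. The stated 30 minutes is therefore consistent with the pulse count. The block fills its 30 minutes, and the unpaired session totals 30 + 30 = 60 min.

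**Step 2: training over 14 days.**

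- Unpaired: 14 × 30 = 420 min (7.0 h).
- Paired or sham: from 14 × (40 − *s*) to 14 × (60 − *s*).

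| Assumed *s* (min/session) | Paired or sham training (min) | Ratio to 420 | Difference |
|---|---|---|---|
| 0 | 560-840 | 1.33-2.00 | +33% to +100% |
| 10 | 420-700 | 1.00-1.67 | 0% to +67% |
| 20 | 280-560 | 0.67-1.33 | −33% to +33% |
| 30 | 140-420 | 0.33-1.00 | −67% to 0% |

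The row *s* = 0 is the natural reading. The other rows need an allowance that the protocol does not give.

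**Step 3: what equality would require.** The non-training time would have to be 40 − 30 = 10 min in the shortest paired session and 60 − 30 = 30 min in the longest. No single allowance does this: at any fixed *s* the range still spans 14 × 20 = 280 min.

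**Step 4: matching on total session time.** The unpaired total of 60 min lies within 40-60, but equals the paired total only when a paired session lasts 60 min. On the natural reading, training is then 60 against 30 min, the widest gap in the table.

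**Step 5: how the test would react (illustration; the shifts are assumed).** Suppose pairing has no effect, but a difference in training shifts mean FMA-UE change by *d* standard deviations. For a two-sided 5% t-test with *n* per group, df = 2*n* − 2 and noncentrality *d*√(*n*/2), the rejection rates are:

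| *d* | *n* = 40 | *n* = 50 |
|---|---|---|
| 0.1 | 7.3% | 7.9% |
| 0.2 | 14.3% | 16.8% |
| 0.3 | 26.3% | 31.8% |
| 0.4 | 42.4% | 50.8% |

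The group sizes are the protocol's 40 before and 50 after its dropout allowance. Nothing in the protocol says which *d*, if any, would apply, so the conclusion does not rest on this table.

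**The case against.** The strongest reply is that the two figures measure different things. The 40-60 minutes belongs to the intervention and the 30 minutes to motor training. Compared like for like, the unpaired intervention is 60 minutes, inside the paired range. The only express statement on comparability says the training is the same, and it stands in the same paragraph as the 30 minutes. A reader could take 30 minutes as the common training time, or take *identical* to mean the same exercises. Non-training time need not be fixed either: setting the amplitude below each patient's pain threshold and working from an EMG trigger could take a different time in each patient. The direction of any bias also depends on the allowance, and the table above runs from +100% to −67%. Finally, the protocol calls the trial exploratory, and the point touches its secondary objective.

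Much of this stands as a limit on the claim. The protocol does not prove unequal training, and both the confounding and its direction depend on the natural reading. The objection does not remove the inconsistency, because none of the benign readings is written down. No passage divides the 40-60 minutes, gives a set-up time, counts training repetitions or says what *identical* refers to. In the unpaired arm, moreover, the intervention is divided wholly into stimulation and training, with nothing set aside for set-up. If the word carries the same meaning in the paired arm, the 40-60 minutes is active time.

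**Conclusion.** The concern holds. The protocol calls the unpaired arm's motor training identical to the paired arm's, but gives times that agree only if 10 to 30 minutes of each paired session is unstated non-training time. With no such time, the paired arm receives 140-420 minutes more training over 14 days (560 − 420 to 840 − 420), in the direction that favours hypothesis 2. The paired-versus-unpaired comparison could not then establish that pairing is necessary.

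Confidence is high that the text is inconsistent as written. The confounding rests on reading 40-60 minutes as training time, and its effect on FMA-UE cannot be sized from the protocol. Paired versus sham is matched on stated session time and is untouched. This should be fixed, but it does not undermine the whole trial.

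**What to change.** 1. Reconcile the paired, unpaired and sham descriptions under Major interventions so that the stated training time in each arm agrees with the word *identical*. Which figure is intended is for the sponsor to decide.
2. State whether 40-60 minutes is session time or training time, and whether *identical* refers to minutes, exercises or repetitions.
3. Record the training minutes delivered at each session in every arm, so that comparability can be shown.
4. If training time is meant to differ, delete *identical* and restate hypothesis 2 and the secondary objective as a comparison of two treatment packages rather than a test of whether pairing is necessary.

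The cost is protocol wording and one field in the session record, with no extra patients. Under item 4 the price is a weaker conclusion for hypothesis 2.

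### The between-arm FMA-UE tests use unadjusted change scores: valid, but generally less precise than adjusting for the baseline score already collected

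*Protocol*

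**What the plan says.** All references are to the Protocol.

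- **Statistical method, 1. Primary endpoints, step (1):** a within-arm "paired sample t-test will be performed before and after the intervention to compare whether there will be a significant change", with a Bonferroni correction.
- **Step (2):** "The FMA-UE scores before and after the intervention will be summed and subtracted to obtain the FMA-UE change scores". I read this as post minus pre. Then "a one-way three-level (paired vs. unpaired vs. pseudo-stimulated) analysis of variance (ANOVA) will be performed on the main intervention effect of the three groups".
- **Step (3):** "Independent samples t-tests will be conducted for the main intervention effects among groups", and "And the main intervention effects of the paired experimental group and the unpaired experimental group will be compared by independent sample t-test". Neither step (2) nor step (3) names a covariate.
- **Research hypothesis:** both hypotheses compare arms. Hypothesis 1 reads "The test group will show significantly greater improvement in upper limb motor function in stroke patients compared to the control group". Hypothesis 2 says that paired stimulation "will be significantly more effective in improving upper limb motor function in stroke patients compared with the unpaired test group".
- **Sample size:** "The sample size for this study was estimated as 40 study patients per group", raised to 50 per arm for 20% dropout, 150 in total. No SD and no baseline/post correlation is given.
- **Evaluating indicator:** FMA-UE is measured before and after the intervention in all three arms.

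**The concern.** Subtracting the baseline score is the same as adjusting for it with a regression slope fixed at 1. When the true slope of post on baseline differs from 1, part of the baseline variation stays in the change score and widens the error term. ANCOVA estimates the slope instead, answers the same between-arm questions, and needs no data that the trial does not already collect. The Protocol prescribes the unadjusted analysis explicitly, so this is a choice it has made and not a detail left to the SAP.

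What is at stake is precision, in a trial sized for about 80% power per comparison. Chance baseline differences between arms are one way the lost precision shows up; they are not an additional harm.

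The smaller point is labelling. Step (1) stands first under the primary endpoint, yet a before/after change within an arm bears on neither hypothesis. Every arm receives motor training, and patients may enter from two weeks after onset, so scores can rise in any arm, sham included, without a device effect. The Bonferroni correction does not alter that.

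**Working it through.** **Reproducing the plan's figure.** Inputs from Sample size: d = 0.632, alpha = 0.05, power 0.80 (the Protocol writes this as beta = 0.80; only power = 0.80, two-sided, gives its n).

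n = 2 × (1.960 + 0.842)² / 0.632² = 39.3, so 40 per arm. Then 40 / 0.8 = 50, and 3 × 50 = 150. By the noncentral t (78 df), power at 40 per arm is 79.7%. At 50 per arm it is 87.9%.

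**Variance of the two analyses.** Set the baseline SD to 1, the post SD to k, and the baseline/post correlation to rho.

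- Change score: 1 + k² − 2·rho·k
- ANCOVA residual: k²(1 − rho²)
- Difference: (1 − rho·k)², which is never negative and is zero only when the slope rho·k equals 1

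With k = 1 the ratio ANCOVA/change is (1 + rho)/2. Example with k = 1.1 and rho = 0.7: 1.21 × 0.51 = 0.617, against 1 + 1.21 − 1.54 = 0.670, a ratio of 0.921.

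**Assumptions not in the Protocol.** d = 0.632 is on the change-score scale; rho is 0.5, 0.7 or 0.9; k is 1 or 1.1.

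**Results at 40 per arm, two-sided 0.05.** The effective effect size under ANCOVA is 0.632/√ratio. Pairwise power is by the noncentral t with 77 df. The CI half-width, in change-score SDs, is t(0.975, 78) × √(2/40) for change scores and t(0.975, 116) × √[(2/40) × ratio × (1 + 1/115)] for the three-arm ANCOVA. The last column is the power of the three-level test when one arm differs by d (analytic for change scores, simulated for ANCOVA).

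| Analysis | k | rho | Variance ratio | Pairwise power | 95% CI half-width | Three-level test |
|---|---|---|---|---|---|---|
| Change score | any | any | 1 | 79.7% | 0.445 | 83.0% |
| ANCOVA | 1.0 | 0.5 | 0.750 | 89.7% | 0.385 | 92.4% |
| ANCOVA | 1.0 | 0.7 | 0.850 | 85.7% | 0.410 | 88.6% |
| ANCOVA | 1.0 | 0.9 | 0.950 | 81.7% | 0.434 | 84.4% |
| ANCOVA | 1.1 | 0.5 | 0.818 | 87.0% | 0.402 | 89.9% |
| ANCOVA | 1.1 | 0.7 | 0.921 | 82.8% | 0.427 | 85.4% |
| ANCOVA | 1.1 | 0.9 | 1.000 | 79.7% | 0.445 | 82.8% |

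At 50 per arm, pairwise power rises from 87.9% to 95.1%, 92.4% and 89.4% with k = 1, and to 93.3%, 90.3% and 87.9% with k = 1.1.

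**Simulation check.** With k = 1 and 40 per arm (20,000 runs per setting), change score against ANCOVA gave 80.1% v 89.2% at rho 0.5, 80.1% v 85.5% at 0.7, and 79.9% v 81.6% at 0.9. Under no effect, rejection rates were 4.7–5.1% for change scores and 4.8–5.3% for ANCOVA, so both hold their per-comparison level.

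**The case against.** The strongest reply is that nothing here is wrong. A change-score ANOVA is valid, it gives the planned power for a single comparison, and the Protocol calls the trial exploratory. That stands, and it is why this is a recommendation about precision only. It does not remove the reason to change: the Protocol fixes the less efficient of two valid analyses. If the slope is near 1, ANCOVA costs essentially one degree of freedom.

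The size rests on assumptions, and this also stands. A 14-day course may well give a high correlation and a small gain; at rho 0.8 with a post SD 10% larger the gain is 1.3 points. The range can also be exceeded. With a post SD 10% smaller than baseline the gain is 8 to 13 points over rho 0.5 to 0.9, and with equal SDs and rho of 0.4 down to 0.2 it is about 12 to 15. So 0 to 10 points describes the stated grid and is not a bound.

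The statements on type I error and sample size hold per comparison at two-sided 0.05. Step (3) states no multiplicity correction for the primary pairwise tests. Three unadjusted tests have a familywise error of about 12% under the global null, and at 0.05/3 the change-score power at 40 per arm is 65%. That is a separate matter which ANCOVA does not settle.

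Finally, the Protocol nowhere claims that the within-arm tests support its hypotheses. True; on its own the labelling point would be cosmetic.

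**Conclusion.** The point holds as a precision issue in the primary analysis, not a validity error. The change-score estimate is unbiased over randomisations, and the 40/50/150 calculation stands for a single two-sided comparison at 0.05. Under the stated assumptions, adjusting for baseline FMA-UE adds about 0 to 10 points of pairwise power at 40 per arm and narrows the 95% CI half-width from 0.445 to between 0.385 and 0.445 change-score SDs. The gain disappears when the post-on-baseline slope is near 1. The choice does not depend on knowing the correlation, because ANCOVA's residual variance is never larger than that of the change score. The change should be made; the trial does not fail without it.

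**What to change.** In Statistical method, 1. Primary endpoints:

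- Replace the unadjusted ANOVA and t-tests in steps (2) and (3) with one pre-specified ANCOVA: post-intervention FMA-UE on arm (three levels) plus pre-intervention FMA-UE. Use the same two scores that step (2) subtracts, and name their visits, since Table 1 schedules FMA-UE at ts, t1, t2 and t3. Taking change as the outcome with the same covariate gives identical arm contrasts.
- Keep the three-level comparison as the adjusted global test of arm.
- Take the paired–sham, unpaired–sham and paired–unpaired contrasts, with 95% CIs, from that model.
- Keep the step (1) paired t-tests, but label them descriptive and not evidence for hypothesis 1 or 2.

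The cost is rewording steps (1) to (3) before unblinding. No patients, visits or measurements are added, and the between-arm comparisons and sample size stay as planned.
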